## Protocol Summary

Investigational drug	Liraglutide Injection	Registration classification	Biology - Class 7
Study title	A multicenter, randomized, double-blinded, placebo-controlled phase III clinical study to evaluate the efficacy and safety of Liraglutide Injection in the intervention of obese or overweight adult patients with associated metabolic abnormalities		
Clinical study approval No.	CXSL1900149		
Sponsor	Wanbang Biopharmaceuticals		
Trial site	Zhongshan Hospital, Fudan University		
PI:	[name]		
Trial phase	III		
Study objective	
Primary study objective
 
To evaluate the body weight loss effect of Liraglutide Injection compared with placebo in obese or overweight adult patients with related metabolic abnormalities (hypertension, dyslipidemia or type 2 diabetes).
 
Secondary study objective:
 
 
● To observe the effect of Liraglutide Injection on waist circumference, blood pressure, blood lipid, blood glucose and other metabolic index and quality of life compared with placebo;
 
● To evaluate the safety and tolerance of Liraglutide Injection.
 
		
Trial design	
This is a multicenter, randomized, double-blind, placebo-controlled phase III clinical trial. The total study duration will be about 34~36 weeks, including a 2-week screening period, a 6~8-week dosage adjustment period, a 24-week stable treatment period and a 2-week safety follow-up period. Subjects with obesity or overweight with related metabolic disorders will be subcutaneously injected with 3.0 mg Liraglutide Injection or placebo every day. Changes in body weight from baseline for Liraglutide Injection will be compared with placebo at the end of treatment. In the course of the trial, the subjects will be weighed on an empty stomach and blood samples will be collected according to the protocol, and the efficacy and safety will be evaluated. All subjects will be given medication on the basis of reduced calorie diet guidance (reduced by about 500 kcal/day) and increased physical exercise.
		

	
The diagram illustrates the study timeline. At the top, two parallel horizontal lines represent the treatment groups: 'Liraglutide Subcutaneous injection' and 'Placebo Subcutaneous injection'. Below these, a large blue double-headed arrow indicates the intervention: 'Reduce 500 Kcal calories daily and increase physical'. The timeline is marked with vertical arrows and brackets. It begins with 'Screening' (2 weeks), followed by 'Randomization' (marked with a vertical arrow). The '6-8 weeks Dosage adjustment' phase follows, then a '24 weeks 3.0 mg/d stable treatment' phase. The study concludes with a '2 weeks Safety follow-up' phase. The y-axis is labeled 'Screening' and 'Randomization'.

Subject population	Obese or overweight adult patients with associated metabolic abnormalities
Sample size	Total 291 subjects will be enrolled as planned, and about 414 subjects will be included in the study as expected considering the dropouts.
Inclusion criteria	
 
1) Those voluntarily participating and signing the ICF.
 
2) Those aged 18-70 years old (including 18 and 70 years old), without restriction on male and female
 
3) Those failing to control their body weight in previous diet therapy alone.
 
4) Those voluntarily following the medication, diet and exercise requirements decided by the investigators.
 
5) Those with a stable body weight (patient reported body weight change < 5 kg) in last 3 months.
 
6) Those with BMI <math>\geq 30</math> kg/m^2 (obese) or BMI <math>\geq 27</math> kg/m^2 (overweight) accompanied by at least one treated or untreated related metabolic abnormality (hypertension, dyslipidemia, type 2 diabetes). Those with untreated hypertension defined as SBP <math>\geq 140</math> mmHg or DBP <math>\geq 90</math> mmHg; untreated dyslipidemia defined as LDL-C <math>\geq 4.1</math> mmol/L, TG <math>\geq 1.7</math> mmol/L, TC <math>\geq 5.7</math> mmol/L or HDL-C < 1.0 mmol/L in male and < 1.3 mmol/L in female.
 
7) Those with type 2 diabetes should additionally meet the following inclusion criteria: 
 
a) Those diagnosed as type 2 diabetes according to WHO (1999) Diagnostic and Classification Criteria at the time of screening;
 
b) Those receiving diet and exercise therapy alone, or receiving metformin, sulfonylureas, glycosidase inhibitors and glinides alone or in combination on the basis of diet and exercise therapy, with their treatment remaining stable at least 3 months before screening (with original documents such as prescriptions provided);
 
c) Those with HbA1c of 7.0-10.0% (inclusive);
 
d) Those with FPG < 13.3 mmol/L (240 mg/dL).
 
 
 

Exclusion criteria	
Subjects who meet one of the following exclusion criteria will be excluded.
 
 
1) Those with type 1 diabetes or secondary diabetes.
 

- 2) Those with acute metabolic complications such as diabetic ketoacidosis or hyperglycemia (coma) within 6 months before screening.
- 3) Those with 2 or more severe hypoglycemia events (hypoglycemia with severe cognitive impairment and need other measures to help them recover) without obvious inducement within 3 months before screening.
- 4) Those receiving GLP-1 receptor agonist, DPP-4 inhibitors, SGLT-2 inhibitor, or insulin therapy within 3 months prior to screening.
- 5) Those with obesity caused by endocrine diseases such as Cushing's syndrome.
- 6) Patients taking drugs that can significantly increase weight in the 3 months before screening, including systemic glucocorticoid (except cumulative or continuous use of less than 14 days).
- 7) Those using OTC weight-loss drugs or appetite inhibitors (including traditional Chinese medicine as weight-loss drugs) within 1 month before screening, or use prescription weight-loss drugs (such as fentanyl, sibutramine, orlistat) or lipid dissolving injection (such as fat dissolving needle) within 3 months before screening.
- 8) Those with binge eating behavior in the past, that is, eating a large amount of food in a short period of time with a sense of loss of control.
- 9) Those who have treated or plan to treat obesity (during the trial) with surgery or body weight loss devices.
- 10) Those with a past or family history of MTC (grandparents, parents, siblings), or those whose genetic diseases are prone to induce MTC and MEN2.
- 11) Those with thyroid nodules of unknown etiology at the time of screening which is considered clinically significant by the investigator (calcitonin is more than 50 pg/ml, which is only allowed to be retested once).
- 12) Those with a past history or found to have hyperthyroidism or hypothyroidism or subclinical hypothyroidism at the time of screening [TSH > 6 mIU/L].
- 13) Those with history of pancreatic cancer, acute or chronic pancreatitis, or with acute or chronic pancreatitis at the time of screening, or having blood amylase or lipase  $\geq 3$  times ULN.
- 14) Those with acute gallbladder disease (cholecystitis, gallstone) more than 2 times in 1 year before screening.
- 15) Those with MDD, anxiety disorder or other mental illnesses or with the PHQ-9 score  $\geq 15$  at screening
- 16) Those with the following cardiovascular and cerebrovascular diseases within 6 months before screening: decompensated cardiac insufficiency (NYHA Class III-IV), UA or AMI, CVA or stroke.
- 17) Those with a history of heart valve replacement, CABG or other PTCA including percutaneous coronary intervention.
- 18) Those who fail to control their blood pressure effectively, with SBP  $\geq 160$  mmHg or DBP  $\geq 100$  mmHg.
- 19) Those with a history of malignancy in the past 5 years, not including cervical epithelial carcinoma, squamous cell carcinoma or basal cell carcinoma of skin that have been clinically cured within 5 years.
- 20) Those with known proliferative retinopathy or maculopathy.
- 21) Those with a history of major surgical operations (intrathoracic, intracranial, intraperitoneal, etc.) within 6 months, or planning to perform operations that may interfere with the completion or compliance of the study.
- 22) Those with a history of organ transplantation.
- 23) Those with ADIS or syphilis at the time of screening, or whose serum virological test shows hepatitis C virus antibody or hepatitis B surface antigen and hepatitis B core antibody are positive at the time of screening.
- 24) Those with AST or ALT > 3.0-fold ULN, or total bilirubin > 2.0-fold ULN at the time of screening.
- 25) Those with eGFR < 60 mL/min/1.73 m^2 at the time of screening.
- 26) Those with a history of drug abuse (heavy and repeated use of dependent drugs or substances not related to medical purposes, including addictive and habitual

	
drugs, causing physical and mental dependence) in 5 years before screening and alcohol dependence (long-term heavy drinking, causing physical and mental dependence, male drinking more than 14 units of alcohol per week, and female drinking more than 7 units per week) (1 unit alcohol = 360 mL beer or 45 mL spirits with 40% alcohol content or 150 mL wine)].
 
27) Female who are known to be pregnant (determined by pregnancy test at the time of screening) or who are breast-feeding or who plan a pregnancy during the study and are unwilling to take effective contraceptive measures (including partners).
 
28) Those participating in other intervention clinical trials within 3 months prior to screening.
 
29) Those known to be allergic to GLP-1 receptor agonist.
 
30) Those with any serious systemic diseases as determined by the investigator, or other diseases as believed by the investigator to be possible to interfere with the results of this study or abnormal laboratory tests with clinical significance.
 
31) Those who, according to the opinion of investigators, are not suitable to participate in clinical trials, including those who are physically or psychologically unable to comply with the protocol.
												
Stratified standard	Based on stratified randomization, stratifying factors included baseline BMI < 30 kg/m  and ≥ 30 kg/m  , presence and absence of type 2 diabetes. The number of enrolled patients with type 2 diabetes should not exceed 17% of the total number.												
Rescue therapy criteria	
If the fasting blood glucose of patients with type 2 diabetes exceeds the following standard (at least 2 times, one of which should be fasting venous blood glucose), the combination of hypoglycemic drugs can be gradually increased to the maximum prescription dose. If the blood glucose is still out of control, other hypoglycemic treatments (metformin, sulfonylureas, glycosidase inhibitors or glinides) permitted by this protocol should be allowed to be increased, which will determined by the investigator.
 
 
● Baseline - Week 6: FPG > 13.3 mmol/L (240 mg/dL)
 
● Week 7~Week 30: FPG > 11.1 mmol/L (200 mg/dL)
 
 
Rescue therapy will affect the evaluation of body weight and response indicators, so the body weight and blood glucose efficacy analysis will only include the measured values before rescue therapy.
												
Administrati on regimen	
Investigational drug: Liraglutide Injection (BID), by subcutaneous injection, with the injection site to be at the abdomen, thigh or upper arm as selected. Dosage adjustment is not required when injection site and injection time change. The initial dose of Liraglutide Injection should be 0.6 mg per day. The dose escalation protocol should be based on the table below to reduce the likelihood of gastrointestinal symptoms. At Week 7, the dose should be increased to 3.0 mg per day. A subject failing to tolerate the target dose of 3.0 mg may try the dose of 2.4 mg and try to increase the dose to 3.0 mg again within 2 weeks. If the subject is still unable to tolerate such dose (3.0 mg), the drug must be discontinued and the treatment must be terminated.
 
Control drug: placebo, which should be used as above.
 
Dose increment protocol for the investigational drug
 
  
 Week	Daily dose	
   
 Week 1	0.6 mg	
 
 Week 2	1.2 mg	
 
 Weeks 3~4	1.8 mg	
 
 Weeks 5~6	2.4 mg	
 
 Week 7	3.0 mg	
  
	Week	Daily dose	Week 1	0.6 mg	Week 2	1.2 mg	Weeks 3~4	1.8 mg	Weeks 5~6	2.4 mg	Week 7	3.0 mg
Week	Daily dose												
Week 1	0.6 mg												
Week 2	1.2 mg												
Weeks 3~4	1.8 mg												
Weeks 5~6	2.4 mg												
Week 7	3.0 mg												
Study cycle	
Screening period: 2 weeks
 
Treatment period: 30~32 weeks (about 6~8 weeks of dosage adjustment period, 24 weeks of stable treatment period)
 
Safety follow-up period: 2 weeks
												

	The study cycle will be about 34~36 weeks.
Response evaluation indicator	
Primary endpoint:
 
 
1) The percentage of body weight loss from baseline at the end of treatment;
 
2) The proportion of subjects whose body weight will decrease by <math>\geq 5\%</math> from baseline level at the end of treatment;
 
 
Secondary endpoint:
 
 
1) Changes in waist circumference of the subjects at the end of treatment;
 
2) Changes in blood pressure level (diastolic pressure and systolic pressure) and pulse of the subjects at the end of treatment;
 
3) The changes in blood lipid levels (triglyceride, total cholesterol, low density lipoprotein cholesterol, and high density lipoprotein cholesterol) of the subjects at the end of treatment;
 
4) The change of blood glucose level (insulin, fasting blood-glucose) of the subjects at the end of treatment;
 
5) The changes in HbA1c of patients with type 2 diabetes at the end of treatment;
 
6) The absolute body weight loss of the subjects at the end of treatment;
 
7) The proportion of subjects with body weight loss <math>> 10\%</math> at the end of treatment;
 
8) Effect of changes in body weight of the patients to the IWQOL-lite at the end of treatment
 

Response evaluation criteria	
The product can be considered to be effective in body weight control when the following conditions are met simultaneously after 30-32 weeks of treatment:
 
 
◇ The difference in mean body weight loss between the experimental group and the placebo group is at least 5%, and the difference is statistically significant.
 
◇ The proportion of subjects losing more than 5% of their body weight from baseline in the experimental group should be at least 35%, which should be about 2 times as much as that in the placebo group. In addition to that, the difference between the two groups should be statistically significant.
 

Safety evaluation index	
It is used to evaluate the safety and immunogenicity of the investigational drug following subcutaneous injection.
 
 
● Incidence rate of AEs, AEs during treatment, serious and non-SAEs
 
● Incidence rate of gastrointestinal reactions: including nausea, diarrhea, vomiting, constipation, abdominal pain and dyspepsia
 
● Incidence rate of hypoglycemic events: proportion of subjects and incidence rate of hypoglycemic events in each category
 
● Early withdrawal due to AEs: including stopping treatment due to nausea and vomiting
 
● Changes in vital signs
 
● Changes in physical examination
 
● Changes in 12 lead ECG
 
● Changes in clinical laboratory examination parameters (blood routine, urine routine, blood biochemistry (liver function, kidney function, TSH, calcitonin, amylase, lipase, etc.))
 
● Changes in PHQ-9
 
● Incidence rate of Liraglutide antibody
 


Sample size calculation
	
According to the statistical requirements of placebo-controlled superiority trial, the main response indicator of this study is the mean weight loss percentage of subjects compared with baseline at the end of treatment and the proportion of subjects with body weight loss <math>\geq 5\%</math> at the end of treatment, and the two indicators will be the synergistic response indicators.
 
According to the response evaluation criteria, the product can be considered effective for body weight control if the following two conditions are met simultaneously at the end of treatment:
 
response indicator (1) The difference in mean body weight loss between the experimental group and the placebo group should be at least 5%, with the difference to be statistically significant. With the bilateral test <math>\alpha=0.05</math> and the power as 90% and without considering the shedding, the random proportion of experimental group: placebo group is 2:1, the required sample size is 102 cases in the experimental group and 51 cases in the placebo group, with a total sample size of 153 cases
 
Response indicator (2) The proportion of subjects with body weight loss <math>\geq 5\%</math> from baseline in the experimental group should be at least 35%, which is about 2 times the body weight loss rate of subjects in the placebo group, with the difference between the two groups to be statistically significant. With the bilateral test <math>\alpha=0.05</math> and the power as 90% and without considering the shedding, the random proportion of experimental group: placebo group is 2:1, the required sample size is 194 cases in the experimental group and 97 cases in the placebo group, with a total sample size of 291 cases.
 
According to the above response evaluation criteria, the above 2 response indicators should be met at the same time in order to succeed in the trial. Therefore, 291 cases of the larger sample size required to achieve statistical significance of the 2 indicators are taken as the effective sample size required for the synergistic response indicator. Taking into account the shedding factors, it is estimated that about 414 subjects will be included according to the 30% shedding rate.


Statistical analysis
	
The software of SAS 9.4 or above will be used for analysis. The safety data set will be used for safety analysis, and the data from the full analysis set and the per protocol set will be used for the analysis of efficacy. The analysis of the primary endpoint will be based on the full analysis set.
 
Collaborative main evaluation indicator of the study 1: The percentage of subjects in the experimental group who lost body weight compared with baseline at the end of treatment. Superiority test hypothesis 1:
 
 
• <math>H_0</math>: The difference in the mean change in body weight between the Liraglutide Injection group and the placebo group at the end of treatment compared with the baseline period is <math>< 5\%</math>;
 
• <math>H_1</math>: The difference between the Liraglutide Injection group and the placebo group at the end of treatment compared with baseline body weight change was <math>\geq 5\%</math>.
 
 
Collaborative main evaluation indicator of the study 2: The proportion of subjects whose body weights decrease by <math>\geq 5\%</math> from baseline at the end of treatment. Superiority test hypothesis 2:
 
 
• <math>H_0</math>: The proportion of subjects who lost more than 5% of their body weight from baseline is less than 35% in the experimental group, or the proportion of subjects in the experimental group lost body weight 2 times as much as that in the placebo group, or there is no statistical significant difference between the two groups.
 
• <math>H_1</math>: The proportion of subjects with body weight loss <math>\geq 5\%</math> from baseline in the experimental group is greater than or equal to 35%, which is 2 times as much as that in the placebo group, and there is a statistical significant difference between the two groups.
 
 
The above two statistical test hypotheses are based on two-sided test, and at the significance level of <math>\alpha=0.05</math>, the two collaborative primary endpoints should reach statistical significance at the same time.
 
The safety evaluation indexes include physical examination, vital signs, electrocardiogram, laboratory examination, immunogenicity, mental health assessment and AEs. The immunogenicity evaluation indicator is the incidence rate of Liraglutide antibody.

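### Read literally, the family-history limb of exclusion criterion 10 does not cover a subject whose child has MTC, although it counts grandparents

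*Combined protocol and SAP*

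**What the plan says.** Exclusion criterion 10 (Protocol Summary, Exclusion criteria) has two limbs. The first concerns the subject's own past and the family: "Those with a past or family history of MTC (grandparents, parents, siblings"). The second concerns the subject's own inherited condition: "or those whose genetic diseases are prone to induce MTC and MEN2".

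The list opens with the rule that meeting any single criterion is enough: "Subjects who meet one of the following exclusion criteria will be excluded". What one criterion fails to name can therefore still be caught by another, and the neighbouring criteria matter here:

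- Criterion 11 concerns thyroid nodules at screening, with a calcitonin condition: "calcitonin is more than 50 pg/ml, which is only allowed to be retested once".
- Criterion 30 concerns serious systemic disease, other disease that might interfere with the results, and clinically significant laboratory abnormalities.
- Criterion 31 leaves a general judgement to the site: "Those who, according to the opinion of investigators, are not suitable to participate in clinical trials".

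Inclusion criterion 2 sets the age range: "Those aged 18-70 years old (including 18 and 70 years old").

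**The concern.** Parents, siblings and children are all first-degree relatives and share about half of the subject's genes. Grandparents are second-degree and share about a quarter. If MTC in a grandparent is informative enough to exclude a subject, MTC in a child is at least as informative about heritable risk. The list keeps the more distant class and drops a nearer one, and the Summary gives no reason for this.

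The criterion is evidently there to keep people with a hereditary risk of MTC out of a trial of this drug, although the Summary does not state that purpose. A site that takes the list literally could record no family history for a subject with an affected son or daughter. What is at stake is the safety screening of that individual subject.

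**Working it through.** The plan gives no figure to reproduce. The check is a reading of the criteria, followed by a short calculation of scale.

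**Step 1. Which relatives are named in criterion 10?**

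| Relative | Degree | Named |
|---|---|---|
| Parents | first | yes |
| Siblings | first | yes |
| Children | first | no |
| Grandparents | second | yes |

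Two of the three first-degree classes are named, together with one second-degree class.

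**Step 2. Is the list open or closed?** Where these criteria give examples they often mark them. Criterion 5 does so: "Those with obesity caused by endocrine diseases such as Cushing's syndrome". Criterion 7 uses 'such as' and criterion 21 uses 'etc.'. Criterion 10 has no marker, so the natural literal reading is that the parenthesis defines the family. The style is not uniform, however. Criterion 14 and inclusion criterion 6 also use bare parentheses; the one in inclusion criterion 6 looks exhaustive, while the one in criterion 14 could be a gloss. The wording favours the closed reading without settling it.

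**Step 3. Would another criterion exclude a subject whose child has MTC?**

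| Route | What triggers it | Covers this subject? |
|---|---|---|
| Criterion 10, second limb | the subject's own predisposing genetic disease | only if that disease is already known |
| Criterion 11 | the subject's own nodules and calcitonin | only if the subject has such findings |
| Criterion 30 | the subject's own diseases or laboratory results | only if present and judged relevant |
| Criterion 31 | the investigator's opinion | permitted, not required |

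No criterion in the list requires exclusion because a child is affected. Every other route is conditional or discretionary.

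**Step 4. Scale.** Let *p* be the proportion of otherwise eligible subjects who have a child with MTC. The documents give no value for *p*.

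- Expected number among about 414 subjects (Protocol Summary, Sample size) = 414 × *p*.
- Allocation is 2:1 (Sample size calculation), so the active arm has 414 × 2/3 = 276 subjects, and the expected number there is 276 × *p*.
- To expect even one such subject in the whole trial, *p* would have to be 1/414, about 0.24%. To expect one in the active arm, it would have to be 1/276, about 0.36%.

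On the assumption that MTC is rare, *p* lies far below these values and the expected number is very low. A subject who did enter this way would have a 2 in 3 chance of active drug over the planned 30 to 32 weeks of treatment.

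**The case against.** The strongest reply is that the operative words are the family history itself, and that the parenthesis only illustrates it. An investigator who learned of an affected child would probably count it, or would use criterion 31. On this view no passage contradicts another, and the sponsor has simply chosen how far family history extends.

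Part of this stands. The list can be read as illustrative, and criterion 14 shows that a bare parenthesis is weak evidence of a closed list. But if the list is open, two sites may decide the same case differently, which is also a reason to settle the wording. Criterion 31 allows exclusion without prompting anyone to ask about children. A choice of scope that takes in grandparents and leaves out children has no apparent rationale.

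Three stronger readings are tempting, and the documents do not support them:

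- *That a subject whose child has MTC is not excluded from the trial.* The text supports only that the family-history limb, read literally, does not exclude that subject. The routes in Step 3 of the working remain.
- *That many subjects will have adult children.* The upper age limit of 70 makes this plausible for some, but the documents give no figure.
- *That the screening history form is deficient.* The form is not in the supplied text, so it may already ask about children.

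**Conclusion.** The point holds as a minor safety correction. Taken literally, the family-history limb of criterion 10 does not cover a child with MTC although it covers a grandparent, and no other criterion makes exclusion mandatory in that case.

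It should not be read as showing that the trial will enrol such subjects. That would need a value for *p*, which the documents do not give, and it would need every conditional and discretionary route to fail.

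The conclusion rests on three assumptions: that sites apply the parenthesis as written; that MTC is rare, so that the expected number of cases is very low; and that no fuller wording elsewhere settles the matter, since only the Protocol Summary could be checked. Sample size, alpha, power and the efficacy analyses are unchanged on any reading.

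**What to change.** Add 'children' to the parenthesis in exclusion criterion 10, so that all first-degree relatives count. Make the same change wherever the criterion is repeated, including any screening or medical-history form that carries the list of relatives. If children were left out on purpose, the protocol should say so and give the reason.

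The cost is one word in the criterion and, if the form needs it, one item there. No procedure or visit is added, and the loss of recruitment is at most negligible.

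### Exclusion criterion 27, as worded in the Protocol Summary, does not exclude a woman who could conceive and refuses contraception but plans no pregnancy

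*Combined protocol and SAP*

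**What the plan says.** The lead-in to the exclusion list in the Protocol Summary makes any single criterion sufficient: "Subjects who meet one of the following exclusion criteria will be excluded".

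Criterion 27 opens with two free-standing grounds: "Female who are known to be pregnant (determined by pregnancy test at the time of screening) or who are breast-feeding". It then adds a third, for those "who plan a pregnancy during the study and are unwilling to take effective contraceptive measures (including partners".

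Three other entries in the summary bear on whether something else closes the gap:

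- Inclusion criterion 4 asks for willingness to comply, but on named subjects only: "Those voluntarily following the medication, diet and exercise requirements decided by the investigators".
- Exclusion criterion 30 concerns serious or interfering disease and clinically significant laboratory abnormalities.
- Exclusion criterion 31 is a general suitability clause: "Those who, according to the opinion of investigators, are not suitable to participate in clinical trials".

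The age criterion (inclusion criterion 2) is "Those aged 18-70 years old (including 18 and 70 years old), without restriction on male and female", and the study cycle gives "Treatment period: 30~32 weeks".

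**The concern.** The usual purpose of a criterion like this is to keep out any woman who could conceive during treatment and will not use contraception. Her intentions about pregnancy do not settle the risk, since unplanned conception is what contraception is there to prevent. As worded, refusing contraception excludes her only if she also plans a pregnancy.

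Sites apply eligibility criteria directly. If one follows the summary literally, a woman who could conceive may be randomised without agreeing to contraception, and whether she is kept out depends on one investigator's judgement. The plan itself excludes women found pregnant at screening, so it already treats exposure in pregnancy as something to avoid. What is at stake is subject safety; no statistical quantity is involved.

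**Working it through.** The check is mainly one of logic. Write, for a female candidate:

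- A = pregnant at screening
- B = breast-feeding
- C = plans a pregnancy during the study
- D = unwilling to use effective contraception

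**Reading the criterion.** Each new ground opens with its own *or who*. In the last ground a single *who* governs both verbs, which are joined by *and*. The criterion is therefore A or B or (C and D).

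**Applying it to a woman who is neither pregnant nor breast-feeding (A = no, B = no):**

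| Plans pregnancy (C) | Refuses contraception (D) | As worded: A or B or (C and D) | With *or*: A or B or C or D |
|---|---|---|---|
| no | no | not excluded | not excluded |
| no | yes | **not excluded** | excluded |
| yes | no | not excluded | excluded |
| yes | yes | excluded | excluded |

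The second row is the gap. The third row is a further oddity: a woman who intends to become pregnant during the study stays eligible if she says she will use contraception.

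**Trying another parse.** Reading the sentence as (A or B or C) and D does not exclude the woman in the second row either, because A, B and C are all false for her. Only replacing *and* with *or* does.

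**Looking for a backstop in the summary.** Inclusion criterion 4 is limited to medication, diet and exercise. Exclusion criterion 30 is about disease and laboratory findings. Exclusion criterion 31 could reach her, but only as a matter of opinion, and it does not mention contraception. Nothing else in the summary requires contraception.

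**Looking for signs of a slip.** Criterion 26 uses a similar *and* between drug abuse and alcohol dependence ("in 5 years before screening and alcohol dependence"), two conditions that would normally each exclude on their own. This makes a translation or drafting slip plausible in criterion 27, but does not prove it.

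**Bounding the exposure.** Any fetal exposure would run from conception to detection or the end of treatment, so it cannot exceed the treatment period. The summary gives 6 to 8 weeks of dose adjustment and 24 weeks of stable treatment:

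- 6 + 24 = 30 weeks; 30 × 7 = 210 days
- 8 + 24 = 32 weeks; 32 × 7 = 224 days

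The sums agree with the stated 30 to 32 weeks. The lower bound is 0 days (no conception, or assignment to placebo). These are limits only, not an estimate of what would happen.

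**The case against.** The strongest reply is that this is an artefact of the English text and not a rule the sponsor chose. The literal reading gives odd results, criterion 26 has the same loose conjunction, and a criterion that mentions contraception and extends it to partners plainly means willingness to use it to count. Many investigators would read it that way. The text examined is also only a summary: the protocol body, any pregnancy testing during treatment and the consent form may contain a clear requirement. For harm to follow, a site would have to apply the wording literally, the investigator would have to leave criterion 31 unused, no other safeguard could be in place, and a conception would have to occur on active drug. The day counts merely restate the length of treatment.

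Much of this stands. It limits the severity, leaves the origin of the *and* open, and means that no claim can be made about the trial's safeguards as a whole. The day counts are outer limits and carry no further information. None of it changes what the criterion says: the reply has to assume that sites will read *and* as *or*, and an eligibility rule on a safety matter should not depend on that.

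It can also be said that excluding women who plan a pregnancy, as a ground of its own, goes beyond the gap described. That is true, but the third row of the table shows why the separate ground is sensible.

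**Conclusion.** The concern holds, as a minor point. On the wording of the Protocol Summary, a woman of childbearing potential who refuses contraception and plans no pregnancy is not excluded by any mandatory criterion; only the discretionary criterion 31 could exclude her. Possible fetal exposure is bounded between 0 and 210 days on a 30-week course, or 0 and 224 days on a 32-week course. The number of women affected cannot be derived from the documents. Women who are pregnant at screening, breast-feeding or willing to use contraception are outside the gap. Endpoints, alpha, power and sample size do not change.

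The conclusion rests on the summary text alone and on a literal reading of it. Whether the *and* was intended is not known. If the original-language text or the protocol body already uses *or*, the defect is confined to the English summary.

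**What to change.** First compare criterion 27 with the original-language text and the protocol body. If those already use *or*, correct the English summary only. Otherwise reword the criterion as four separate grounds joined by *or*:

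- (a) pregnant, by pregnancy test at screening;
- (b) breast-feeding;
- (c) planning a pregnancy during the study;
- (d) of childbearing potential and unwilling to use effective contraception (including partners) during the study.

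Define childbearing potential in (d). Women are eligible up to age 70, and simply swapping *and* for *or* would exclude postmenopausal or sterile women who have no reason to use contraception. It would also help to say in (d) whether abstinence counts as effective contraception.

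The cost is the rewording of one criterion and possibly a few more screen failures.
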